5.5.1.4. Health Related Quality of Life (HRQOL) Measures

IBDQ

The Inflammatory Bowel Disease Questionnaire (Irvine et al, 1994) is a 32-item questionnaire specifically designed for participants with IBD. The range of the total IBDQ score is 32 to 224. Higher scores indicate better quality of life. The total IBDQ score has 4 dimension scores (bowel, systemic, social, and emotional). Each of the individual IBDQ dimensions will be calculated when ≤ 1 item is missing in the dimension. The missing item will be estimated using the average value across the nonmissing items. If any one of the dimensions within the total IBDQ score cannot be calculated, then the total IBDQ score cannot be calculated.

PROMIS-29

The PROMIS-29 is a validated general health profile instrument that is not disease-specific. It is a collection of short forms containing 4 items for each of 7 domains (depression, anxiety, physical function, pain interference, fatigue, sleep disturbance, and ability to participate in social roles and activities). PROMIS-29 also includes an overall average pain intensity 0-10 numeric rating scale (NRS). They assess all domains over the past seven days except for Physical Function which has no timeframe specified.

The raw score of each domain is converted into a standardized score with a mean of 50 and a standard deviation (SD) of 10 (T-Score). The standardized T-score is reported as the final score for each participant. Pain Intensity is presented as raw responses (0-10). For PROMIS domains of Depression, Anxiety, Physical Function, Pain Interference, and Fatigue, a score of 50 is the average for the United States general population with a standard deviation of 10, because testing was performed on a large sample of the general population. However, the other two domains (Ability to Participate in Social Roles and Activities and Sleep Disturbance) were not centered in a national sample. For these two domains, a score of 50 represents the average of the calibration sample which was generally more enriched for chronic illness, and a score of 50 likely represents somewhat sicker people than the general population. For symptom-oriented domains of PROMIS-29 (anxiety, depression, fatigue, pain interference, and sleep disturbance), higher scores represent worse symptoms and a T-score of 60 is one SD worse than average. For the function-oriented domains (physical functioning and social role), higher scores represent better functioning and a Tscore of 60 is one SD better than average. Additionally, the physical component summary score (PCS) and mental component summary score (MCS) will each be derived from all 7 domain scores of PROMIS-29 (reference) as measures for general health related quality (HRQOL). Higher PCS and MCS scores indicate better HRQOL.

5.5.1.5. Histologic assessment

Histologic assessment will be performed using biopsy samples collected during endoscopy. Two biopsy samples from each of the 5 segments will be collected at screening, Week 12, Week 48, and Week 96 from each of 5 predefined anatomic locations: ileum, right colon, transverse colon, left colon, and rectum.

Biopsies will be collected from representative areas that are consistent with the mucosal appearance visually observed during endoscopy. In a segment with ulcers, all biopsies will be taken from the edge of the ulcer. In a segment without ulcers but with macroscopically abnormal areas, biopsies will be taken from the most inflamed area. In a segment that is endoscopically normal, random biopsies will be taken.

Histologic assessment will be conducted by a group of central expert pathologist readers who are blinded to treatment groups, sites and visits. The modified Global Histology Activity Score (GHAS), Geboes grading scale and Robarts Histologic Index (RHI) will be used to evaluate histologic improvement.

Modified Global Histology Activity Score

The Global Histology Activity Score was first described in 1998, and has been subsequently utilized in a number of studies resulting in peer-reviewed publications (D'Haens et al 1998; D'Haens et al 1999; Mojtahed et al 2014; Baert et al 1999; Laharie et al 2011; Mantzaris et al 2009).

All biopsies for each region will be scored in a blinded manner using the GHAS, with minor adaptations for the circumstances of this study:

- At each time point, all biopsies (up to 2 biopsies per region) obtained from each of the predefined anatomic regions will be scored separately for each of the 8 histological features; feature 8 has been modified from the original GHAS:
 - 1. epithelial damage (scored 0-2)
 - 2. architectural changes (scored 0-2)
 - 3. infiltration of mononuclear cells into the lamina propria (scored 0-2)
 - 4. polymorphonuclear cells in the lamina propria (scored 0-2)
 - 5. polymorphonuclear cells in the epithelium (scored 0-3)
 - 6. the presence of erosions/ulcers (1 for presence and 0 for absence)
 - 7. presence of granulomas (1 for presence and 0 for absence)
 - 8. percentage of the tissue affected on the slide image(s) (0 for none, 1 for >0 and <33%, 2 for 33-66%, and 3 for >66%); blinded readers will assess the percentage of tissue involved, considering both biopsies for a given segment (note that in the original GHAS, this component was measured as "number of biopsies affected")
- For items 1-7, the single highest scoring feature from each of the biopsies will be used as the score for that feature.
- The sum of the scores from the 8 histologic features within a region (terminal ileum, right colon, transverse colon, left colon, rectum) will be used as the Total score for that region (range 0-16). Furthermore,

CONFIDENTIAL – FOIA Exemptions Apply in U.S.

Total Ileum:

- The Ileal score will be equal to the Total Ileum Score.
- If any of the items 1-8 is missing, the Total Ileal score is missing. However, if items 1, 4, 5, and 6 are non-missing, then histologic ileal remission (defined in the Table below) can still be determined.

Total Colonic score:

- The worst available scores for each feature across the right colon, transverse colon, left colon, and rectum will be summed to obtain a Total Colonic score.
- If the worst score across the right colon, transverse colon, left colon, and rectum for any of the items 1-8 is missing, then the Total Colonic score is missing. However, if items 1, 4, 5, and 6 are non-missing, then histologic colonic remission (defined in the Table below) can still be determined.

Total Subject score:

- The worst available scores for each feature across the 5 regions will be summed to obtain a Subject Score
- If the worst score across the ileum, right colon, transverse colon, left colon, and rectum for any of the items 1-8 is missing, then the Total Subject score is missing. However,
 - If items 1, 4, 5, or 6 corresponding to the subject are non-missing, then histologic remission can be determined.
 - If items 1, 4, 5, and 6 corresponding to the subject are all non-missing and all equal to 0 (Q1=Q4=Q5=Q6=0), then the participant is considered to be in histologic response even in the presence of missing scores for items 2, 3, 7, and 8; otherwise, histologic response cannot be determined if at least one of items 2, 3, 7 or 8 is missing.

If both biopsies within a region (ileum, right colon, transverse colon, left colon and rectum) are missing or unevaluable, the GHAS score will be missing for that region.

The definitions of baseline disease activity and histologic remission using the GHAS System apply to a segment (region), Ileal, Colonic, and Subject level; the range of possible scores is 0 - 16 irrespective of extent of the area being analyzed. The binary (yes or no) endpoints histologic response, histo-endoscopic response, and histo-endoscopic remission will be evaluated on a subject level only.

Term	Scope	Definition
Baseline Active Disease (GHAS)	Subject-level	GHAS with a score > 0 for infiltration of
	Ileal Colonic	polymorphonuclear cells in the lamina propria, polymorphonuclear cells in epithelium, or presence of erosions and/or ulcers $[Q1 > 0 \text{ or } Q4 > 0 \text{ or } Q5 > 0 \text{ or } Q6 > 0]$
Histologic Response (GHAS)	Subject-level	\geq 50% reduction in subject-level GHAS score from baseline, or absence of mucosal neutrophils (epithelium and lamina propria), epithelial damage, erosions and ulceration [Q1 = 0, Q4 = 0, Q5 = 0 and Q6 = 0]

Histologic Remission (GHAS)	Subject-level Ileal Colonic	Absence of mucosal neutrophils (epithelium and lamina propria), epithelial damage, erosions and ulceration [Q1 = 0, Q4 = 0, Q5 = 0 and Q6 = 0]
Histo-Endoscopic Response (GHAS)	Subject-level	Combination of histologic response and endoscopic response (≥50% improvement from baseline in SES-CD score)
Histo-Endoscopic Remission (GHAS)	Subject-level	Combination of histologic remission and endoscopic remission (SES-CD \leq 4 and at least a 2-point reduction from baseline and no subscore greater than 1 in any individual component)
Histo-Endoscopic Remission (GHAS, Alternative Definition)	Subject-level	Combination of histologic remission and endoscopic remission (SES-CD Score <2).

Geboes Grading System

Histological disease activity will be scored in a blinded manner by an experienced pathologist using the Geboes Scoring system (GS). The GS is a 7-item scale (with 4 levels of severity for each item) that categorizes inflammation as grade 0 (architectural change only), grade 1 (chronic inflammation), grade 2 (2a, lamina propria eosinophils and 2b, lamina propria neutrophils), grade 3 (neutrophils in the epithelium), grade 4 (crypt destruction), or grade 5 (erosion or ulceration), as illustrated in Table 5.

Grade 0	Structural (architectural change)
Subgrades	
0.0	No abnormality
0.1	Mild abnormality
0.2	Mild or moderate diffuse or multifocal abnormalities
0.3	Severe diffuse or multifocal abnormalities
Grade 1	Chronic inflammatory infiltrate
Subgrades	
1.0	No increase
1.1	Mild but unequivocal increase
1.2	Moderate increase
1.3	Marked increase
Grade 2	Lamina propria neutrophils and eosinophils
2A Eosinophils	
2A.0	No increase
2A.1	Mild but unequivocal increase
2A.2	Moderate increase
2A.3	Marked increase
2B Neutrophils	
2B.0	None
2B.1	Mild but unequivocal increase
2B.2	Moderate increase
2B.3	Marked increase
Grade 3	Neutrophils in epithelium
3.0	None
3.1	< 5% crypts involved
3.2	< 50% crypts involved
3.3	> 50% crypts involved
Grade 4	Crypt destruction
4.0	None
4.1	Probable-local excess of neutrophils in part of crypt
4.2	Probable-marked attenuation
4.3	Unequivocal crypt destruction
Grade 5	Erosion or ulceration
5.0	No erosion, ulceration, or granulation tissue
5.1	Recovering enithelium+adjacent inflammation
5.2	Probable crosion—focally stripped
5.3	Unequivocal erosion
5.4	Ulcer or granulation tissue

Table 5:Grading Criteria for the histological evaluation of Disease Activity in CD
(Geboes grading system)

- At each time point, all biopsies (up to 2 biopsies per region) obtained from each of the predefined anatomic regions will be scored separately for each of the 7 items:
- The single highest scoring item from each of the biopsy will be used as the score for that item.
- The Ileal score is equal to the highest grade with a score > 0 (eg, a score of 3 for Grade 5 will be a 5.3 regardless of the scores for the other grades). All items within the ileum must be non-missing to obtain an Ileal score.
- The Colonic score is equal to the highest grade with a score > 0 across the right colon, transverse colon, left colon, and rectum.
- The Subject score is equal to the highest grade with a score > 0 across the ileum, right colon, transverse colon, left colon, and rectum.

If both biopsies within a region are missing or unevaluable, the GS will be missing for that region. The definitions of baseline disease activity and histologic remission using the Geboes Scoring

System apply to a segment (region), Ileal, Colon, and Subject level. Histologic response, histoendoscopic response, and histo-endoscopic remission will be evaluated on a subject level only.

Term	Scope	Definition
Active Disease (GS)	Subject-level	>2B.0 [Grade 2B \neq 0 OR Grade 3 \neq 0 OR Grade 4 \neq 0 OR
	Ileal	Grade $5 \neq 0$]
	Colonic	
Histologic Response (GS)	Subject-level	\leq 3.1, indicating neutrophil infiltration in <5% of crypts, no crypt destruction and no erosions, ulcerations or granulation tissue)
Histologic Remission (GS)	Subject-level	\leq 2B.0 (i.e., no increase in neutrophils in lamina propria [GS
	Ileal	destruction [GS 4.0], and no erosions, ulcerations or
	Colonic	granulation tissue [GS 5.0])
Histo-Endoscopic	Subject-level	Histologic response and endoscopic response (≥50%
Response (GS)		improvement from baseline in SES-CD score)
Histo-Endoscopic Remission (GS)	Subject-level	Histologic remission and endoscopic remission (SES-CD ≤ 4 and at least a 2-point reduction from baseline and no subscore greater than 1 in any individual component)
Histo-Endoscopic Remission (GS, Alternative Definition)	Subject-level	Histologic remission and endoscopic remission (SES-CD Score ≤2).

Robarts Histologic Index

Histological disease activity will be scored by a blinded experienced pathologist using the Robarts Histopathology Index (RHI). The RHI is a 4-item index (with 4 levels for each item) that evaluates chronic inflammation, lamina propria neutrophils, neutrophils in the epithelium, and erosion or ulceration as illustrated in Table 6. Total score ranges from 0 to 33, where higher scores denote more severe inflammation.

Table 6: Robarts Histologic Index

Component

- 1. Chronic inflammatory infiltrate
- 0=No increase
- 1=Mild but unequivocal increase
- 2=Moderate increase
- 3=Marked increase

2. Lamina propria neutrophils

- 0=None
- 1=Mild but unequivocal increase
- 2=Moderate increase
- 3=Marked increase

3. Neutrophils in epithelium

0=None

1=<5% crypts involved

2=<50% crypts involved

3=>50% crypts involved

4. Erosion or ulceration

0=No erosion, ulceration or granulation tissue

1=Recovering epithelium+adjacent inflammation

1=Probable erosion—focally stripped

2=Unequivocal erosion

3=Ulcer or granulation tissue

RHI = 1 x chronic inflammatory infiltrate level (4 levels)

+ 2 x lamina propria neutrophils (4 levels)

+ 3 x neutrophils in epithelium (4 levels)

+ 5 x erosion or ulceration (4 levels)

That is, RHI incorporates four components from the Geboes score (Grades 1, 2B, 3, and 5) into a weighted sum of the subgrades using the following formula,

RHI = 1*GS1 + 2*GS2B + 3*GS3 + 5*GS5

All components need to be scored with the re-parameterized grade score (Grade 5) to calculate the RHI.

If any of the components needed to calculate the RHI is missing, then the RHI will be set to missing.

All components need to be scored with the re-parameterized grade score (Grade 5) to calculate the RHI.

- At each time point, all biopsies (up to 2 biopsies per region) obtained from each of the predefined anatomic regions will be scored separately for each of the 4 items:
- The single highest scoring item from each of the biopsies will be used as the score for that item.
- The weighted sum of the 4 scores within a region will be used as the Total score for that region (range 0-33). Furthermore,
 - The Ileal score will be equal to the Total Ileum Score
 - The worst scores for each item across the right colon, transverse colon, left colon, and rectum will be summed to obtain a Total Colonic Score.
 - The worst scores for each item across the 5 regions will be summed to obtain a Subject Score.

If both biopsies within a region are missing or unevaluable, the RHI will be missing for that region.

The definitions of baseline disease activity and histologic remission using RHI apply to a segment (region), Ileum, Colon, and Subject level. Histologic response, histo-endoscopic response, and histo-endoscopic remission will be evaluated on a subject level only.

Term	Scope	Definition			
Active Disease (RHI)	Subject-level	RHI with a score > 0 for any of Items 2-4 of RHI (lamina propria			
	Ileal	neutrophils, neutrophils in epithelium, or erosions or ulcerations)			
	Colonic				
Histologic Response (RHI)	Subject-level	\geq 50% reduction in RHI score from baseline or sub-scores of lamina propria neutrophils and neutrophils must be equal to 0, with no ulcers or erosions			
Histologic Remission	Subject-level	sub-scores of lamina propria neutrophils, neutrophils in the			
(RHI)	Ileal	epithelium and erosions or ulcerations must be equal to 0.			
	Colonic				
Histo-Endoscopic Response (RHI)	Subject-level	Histologic response and endoscopic response (≥50% improvement from baseline in SES-CD score)			
Histo-Endoscopic Remission (RHI)	Subject-level	Histologic remission and endoscopic remission (SES-CD ≤4 and at least a 2-point reduction from baseline and no subscore greater than 1 in any individual component)			
Histo-Endoscopic	Subject-level	Histologic remission and endoscopic remission (SES-CD Score			
Remission (RHI		≤2).			
Alternative Definition)					

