Endoscopic assessments of the intestinal mucosa will be evaluated during ileocolonoscopy in all participants. A video ileocolonoscopic examination will be performed at the time points specified in the SoA (Section 1.3). Video endoscopies will be assessed by a central facility that will be blinded to treatment group and visit. A complete video endoscopic examination does not require assessment of the terminal ileum if it cannot be visualized. The SES-CD score will be used to evaluate Endoscopic Improvement (Daperno 2004). The SES-CD is based on the evaluation of 4 endoscopic components (presence/size of ulcers, proportion of mucosal surface covered by ulcers, proportion of mucosal surface affected by any other lesions, and presence/type of narrowing/strictures) across 5 ileocolonic segments. Each endoscopic component is scored from 0 to 3 for each segment, resulting in a total score of up to 15 for each component, except for the narrowing component which can only attain a maximum total score of 11 because by definition, the presence of a narrowing that cannot be passed can be only observed once. In summary, an overall total SES-CD score is derived from the sum of all the component scores and can range from 0 to 56. Endoscopic healing, which is traditionally defined as the resolution (absence) of mucosal ulcers in response to a therapeutic intervention, will also be assessed.

Histologic assessments will be performed using biopsy samples collected during ileocolonoscopy. Biopsy samples will be collected at the time points specified in the SoA (Section 1.3) from the predefined anatomic locations as described in the biopsy manual. The biopsy samples collected post-baseline will be obtained near where the screening biopsy samples were collected, as clinically feasible. Refer to the biopsy manual for details on the biopsy sample collection.

Histologic assessments will be conducted by a central reader who is blinded to treatment group, participant number, and visit. Type of histology analyses will be specified in the SAP.

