5.5.2.10. Histologic assessments

Histologic endpoints - GHAS

- Change from baseline in the Ileal GHAS score at Week 12, Week 48, and Week 96 (among participants with Ileal histologic disease at baseline per GHAS)
- Change from baseline in the Colonic GHAS score at Week 12, Week 48, and Week 96 (among participants with Colonic histologic disease at baseline per GHAS)

- Statistical Analysis Plan Amendment 1 CNTO1959CRD3004
- Change from baseline in the Subject GHAS Score at Week 12, Week 48, and Week 96 (among participants with histologic disease at baseline per GHAS)
- GHAS-determined Histologic response at Week 12, Week 48, and Week 96 (among participants with histologic disease at baseline per Subject GHAS score)
- GHAS-determined Histologic ileal remission at Week 12, Week 48, and Week 96 (among participants with Ileal histologic disease at baseline per Ileal GHAS score)
- GHAS-determined Histologic colonic remission at Week 12, Week 48, and Week 96 (among participants with colonic histologic disease at baseline per Colonic GHAS score)
- GHAS-determined Histologic remission at Week 12, Week 48, and Week 96 (among participants with histologic disease at baseline per Subject GHAS score)
- GHAS-determined Histo-endoscopic response at Week 12, Week 48, and Week 96
- GHAS-determined Histo-endoscopic remission at Week 12, Week 48, and Week 96
- GHAS-determined Histo-endoscopic remission (Alternative definition) at Week 12, Week 48, and Week 96

Histologic endpoints - Geboes

- Geboes-determined Histologic response at Week 12, Week 48, and Week 96 (among participants with histologic disease at baseline per Subject Geboes score)
- Geboes-determined Histologic ileal remission at Week 12, Week 48, and Week 96 (among participants with Ileal histologic disease at baseline per Ileal Geboes score)
- Geboes-determined Histologic colonic remission at Week 12, Week 48, and Week 96 (among participants with colonic histologic disease at baseline per Colonic Geboes score)
- Geboes-determined Histologic remission at Week 12, Week 48, and Week 96 (among participants with histologic disease at baseline per Subject Geboes score)
- Geboes-determined Histo-endoscopic response at Week 12, Week 48, and Week 96
- Geboes-determined Histo-endoscopic remission at Week 12, Week 48, and Week 96
- Geboes-determined Histo-endoscopic remission (Alternative definition) at Week 12, Week 48, and Week 96

Histologic endpoints – RHI

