The estimates of the treatment difference between the combined guselkumab group or each guselkumab group versus the placebo group will be provided by the difference in the least squares means (LSmeans). The 95% confidence interval (CI) for the differences in LSmeans and p-values will be calculated based on the MMRM. An unstructured covariance matrix for repeated measure within a subject will be used. The F-test will use Kenward-Roger's approximation for degrees of freedom. In case of lack of convergence, empirical structured covariances will be used in the following order until convergence is reached: 1) Toeplitz 2) first order Autoregressive Moving Average. If the normality assumption is in question, an appropriate transformation will be used.

Continuous endpoints involving SES-CD or histologic endpoints that are measured only at Week 12 will be compared using an analysis of covariance (ANCOVA) with treatment as a fixed factor, and baseline score, CDAI (\leq 300 or > 300), baseline SES-CD (\leq 12 or > 12), and Bio-Failure status (yes or no) as covariates. Continuous endpoints involving SES-CD will not include SES-CD strata in the model. Multiple imputation (MI) will be used for imputing missing Total SES-CD data under the assumption that the data are missing at random (MAR). For continuous endpoints involving GHAS and RHI, no imputation will be performed for missing GHAS or RHI values; the missing values will remain as missing. For binary endpoints, NRI will be used to impute missing GHAS, Geboes and RHI endpoints.

After Week 24

Two exploratory endpoints (clinical remission at Week 48, endoscopic response at Week 48) will be controlled for multiplicity. The analyses of the two endpoints will be placed after the 6 sequential tests of the co-primary and secondary endpoints in the multiple testing procedure described in Section 5.4.3.1. If all 6 p-values are <0.05, the testing procedure will continue with the 4 tests of these two endpoints (clinical remission at Week 48, endoscopic response at Week 48, for both dose groups) using the Hochberg procedure (Y Hochberg, Biometrika (1988), 75, 4, pp.800-2) with a 2-sided alpha of 0.05. The Type I error will be controlled over the co-primary, secondary, and these two Week 48 exploratory endpoints in this multiplicity-controlled testing procedure.

The testing of other exploratory endpoints will not be controlled for multiplicity, and nominal p-values will be provided.

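### Subject-level and colonic GHAS can score histologic remission or response when the region that was active at baseline has no evaluable tissue at follow-up

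*SAP*

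**What the plan says.** SAP 5.5.1.5 defines the GHAS Subject score feature by feature: "The worst available scores for each feature across the 5 regions will be summed to obtain a Subject Score". The Total Colonic score does the same over the right, transverse and left colon and the rectum. When neither biopsy of a region can be read, "the GHAS score will be missing for that region", and only for that region. On determinability the SAP says: "If items 1, 4, 5, or 6 corresponding to the subject are non-missing, then histologic remission can be determined". Remission means that these four features all score zero. Response means remission or a reduction of at least half in the subject score.

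SAP 5.5.2.10 lists separate ileal, colonic and subject-level remission endpoints, each among participants with histologic disease at baseline at that level. SAP 5.5.3 handles gaps in the binary endpoints as follows: "For binary endpoints, NRI will be used to impute missing GHAS, Geboes and RHI endpoints". On the continuous scores the same section says: "For continuous endpoints involving GHAS and RHI, no imputation will be performed for missing GHAS or RHI values".

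Protocol 8.1 states: "A complete video endoscopic examination does not require assessment of the terminal ileum if it cannot be visualized". Protocol 5.1 (criterion 4) admits isolated ileal disease with its own SES-CD threshold.

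For Geboes, SAP 5.5.1.5 uses as subject score the top non-zero grade found in any of the five regions. The RHI subject score takes the worst item scores over the five regions. Neither text says what happens at subject level when one region is missing.

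**The concern.** A maximum over whatever regions were sampled can only fall, never rise, when a region drops out. If the missing region carried the disease, the drop looks like healing. The participant is then scored a success on tissue that was already clean at baseline, and NRI never applies because the endpoint is not missing.

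At stake are the arm-level GHAS remission and response proportions at Weeks 12, 48 and 96, the change in the continuous subject or colonic score, and the GHAS histo-endoscopic endpoints when the unreached segment also drops out of SES-CD. The main SES-CD approach in SAP 5.3.1 sums only the segments scored at that visit. The SAP does provide a supportive baseline-segment-matched analysis for SES-CD, but histology has no counterpart.

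**Working it through.** **Check of the scale.** The item maxima in SAP 5.5.1.5 sum to 2+2+2+2+3+1+1+3 = 16, which reproduces the stated 0-16 range.

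**Test participant, ileum-only disease.** Baseline ileum items 1 to 8 are 2, 1, 2, 2, 2, 1, 0, 2 (sum 12), with all colonic regions 0. At follow-up there is no evaluable ileal tissue and all colonic regions are 0. Applying the rules literally:

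| Score | Baseline | Follow-up | Result |
|---|---|---|---|
| Subject | 12 | 0 | remission yes, response yes; change of -12 enters as observed |
| Ileal | 12 | missing | remission no, by NRI; change left missing |
| Colonic | 0 | 0 | not active at baseline, so outside the colonic denominator |

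The participant is in both the subject-level and the ileal denominator. The clause that makes the Subject score missing when the worst score for an item is missing does not help: a worst available score is missing only if no region has that item.

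**Same case with the right colon as the only diseased and unsampled region.** Subject and Colonic scores both go from 12 to 0 and both count as remission. The participant is outside the ileal denominator, so no other endpoint shows the discrepancy.

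**Response with disease in two places.** Take the same ileum (12) and colonic items 1, 0, 1, 1, 1, 0, 0, 1 (sum 5), none above the ileal value. The baseline Subject score is 12. With the ileum unsampled and the colon unchanged, follow-up is 5. The reduction is (12-5)/12 = 58%, so response is met with no improvement observed anywhere.

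**Effect on proportions.** Let q be the share of an arm whose status depends on the rule and p the remission rate in the rest.

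- Current rule: (1-q)p + q.
- Missing, then NRI: (1-q)p.
- The arm-level gap between the rules is q.
- With equal q in both arms, the risk difference is (1-q)(pT - pC) under both rules. On an assumed 20-point difference, q = 6% gives 0.94 x 20 = 18.8 points either way.
- With unequal q, the two rules differ by qT - qC. For example, with 20% ileum-only disease and 5% versus 10% unsampled, q is 1% versus 2% and the rules differ by 1 point.

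In ileum-only disease, equal non-sampling gives equal q as long as the colon stays clean equally often. In multi-region disease q also depends on how often the sampled regions clear, so the condition is best stated in terms of q.

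**Size of q.** The documents give neither the share with ileum-only histologic disease nor the share unsampled at follow-up. Assuming 10-30% and 5-20%, and independence: 0.10 x 0.05 = 0.5%; 0.20 x 0.10 = 2%; 0.30 x 0.20 = 6% of participants with histologic disease at baseline.

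**The case against.** The strongest reply is that the plan does ask for the tissue. SAP 5.5.1.5 calls for two biopsies from each of five segments at every endoscopy, and Protocol 8.1 asks for post-baseline samples near the screening sites where feasible. That is right about collection, and it should keep q small. It does not settle the scoring once tissue is absent.

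A reader might go further than the documents allow in four ways.

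- **That the treatment contrast is shrunk or inflated.** With equal q the point estimate of the risk difference does not depend on which rule is used. Non-sampling may follow disease, since a narrowing that cannot be passed blocks access, but nothing in the documents says in which arm or by how much.
- **That the SAP contradicts its own NRI rule.** It does not. NRI applies to missing endpoints, and under the GHAS rule this endpoint is determinable. NRI is bypassed, and endpoints defined at different anatomical levels may legitimately differ.
- **That Geboes and RHI behave in the same way.** Only GHAS refers to available scores. For the other two this is a possible reading, not stated text.
- **That a large relative inflation of placebo remission can be quoted.** No histologic remission rate is given, and the denominator is participants with baseline histologic disease, not all 318.

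It also stands that composite intercurrent events already make many such participants nonresponders, and that some unsampled regions will truly have healed. The histo-endoscopic endpoints are exposed only when the segment is not reached. If it is seen but not biopsied, SES-CD still counts it.

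**Conclusion.** The point holds for GHAS at subject and colonic level. As written, the rule can count an unobserved diseased region as success. For ileum-only disease this gives remission at subject level and failure at ileal level in the same person.

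Compared with NRI, arm-level proportions are higher by q, illustratively 0.5-6 percentage points among participants with baseline histologic disease. That range rests on assumed inputs, covers remission in ileum-only disease alone, and supposes clean sampled regions and no composite intercurrent event. The risk difference changes between rules only by the difference in q between arms, chiefly through unequal non-sampling.

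These endpoints are exploratory and uncontrolled for multiplicity (SAP 5.5, 5.5.3). The co-primary, secondary and two multiplicity-controlled Week 48 endpoints are untouched. The correction is worth making because it is nearly free and the SAP already applies matching logic to SES-CD.

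**What to change.** In SAP 5.5.1.5, state that subject-level and colonic GHAS remission and response need evaluable biopsies from every region (within that level) with active histology at baseline. If one is missing, the status is missing and NRI applies, unless an available region already shows activity, in which case the participant is not in remission. In the test case this gives no remission and no response, in line with the ileal endpoint.

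Set the continuous Subject or Colonic score to missing in the same situation. Carrying the baseline score forward would restore 12 in the test case, but it conflicts with the no-imputation rule in SAP 5.5.3.

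State the same rule for Geboes and RHI. Also align the conjunction in the determinability sentence: the subject-level rule joins items 1, 4, 5 and 6 with *or*, the ileal and colonic rules with *and*.

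If a database lock has passed, run the rule as a sensitivity analysis. The cost is a few SAP sentences and some programming. The downside is slightly lower histologic rates, and some participants whose unsampled region truly healed will count as nonresponders.
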